### **Baseline and yearly measurements**

Height and weight: electronic scale with women in light clothes and without shoes. In a sample of cases body fat and lean mass will be measured with bioelectric impedance.

Blood pressure: electronic device.

Serum glucose, triglycerides and cholesterol: standard quality controlled laboratory techniques Serum Testosterone and Insulin: Radioimmunoassay (RIA). For testosterone we shall use a direct RIA kit which has been validated by comparison with indirect assay after organic extraction of serum samples and celite purification (44).

For a sample of patients, we plan to apply for further financial support to measure several other metabolic, endocrine and inflammation markers (estrogens, SHBG, IGF-I, IGFBP 1, 2 and 3, C-reactive protein, leptin and adiponectin) as well as the DNA polymorphism and RNA expression of several relevant gene, in collaboration with the Dept of Oncology of the Ospedale Civico ARNAS in Palermo and at the Institute of Endocrinology at the Milan University.

### Compliance

Compliance will be monitored through lifestyle compliance questionnaires, dietary questionnaires, weight change and plasma glucose, triglycerides, cholesterol, insulin, testosterone changes after one year of intervention. As adjuvant treatment may alter these biomarkers' level and confound the effect of the intervention, we shall compare blood samples collected in the same treatment phase: at least 3 months after the end of chemotherapy, if any, and 3 months after the start of hormonal therapy, if any, and one year later.

Altering the proportion of energy from dietary carbohydrate and fat has been shown to affect plasma lipid concentrations in controlled feeding studies. As we recommend to obtain carbohydrates from low glycemic index food, however, we do not expect any increase in

triglycerides. We expect a substantial reduction of total and LDL cholesterol and fasting glycaemia, minor changes in HDL cholesterol and triglycerides, and a substantial reduction of body weight and waist circumference in the intervention group compared with the control group. Total cholesterol change is an estimate of saturated fat intake change. Testosterone and insulin are also expected to decrease in subsequent samples, which will be assayed in the same batch. A compliance score will be computed, based on the direction of change in all these biomarkers.

#### Follow-up and outcome events

The main outcome will be new BC events including: - new primary breast cancer

- local/regional recurrence
- distant/metastatic recurrence

The follow up will be based on the routine clinical follow-up at the collaborating hospitals, the periodic questionnaires to study participants, the regional cancer registry and hospital discharge diagnosis system, and death certificates

#### **Statistical power**

The survival of BC patients in Italy is dramatically increasing: 5-year relative survival increased from 80.6% for patients diagnosed in the early 1990s (Berrino et al, EUROCARE-3) (45) to 85.6% for patients diagnosed in the early 2000s (EUROCARE-4, unpublished). For these patients the estimated relapse free survival is 81.9 (EUROCARE high resolution study, unpublished). Such a survival improvement is accompanied by a postponement of the incidence of relapse (table 4). *Table 4. incidence rate of local + distant recurrences (EUROCARE, unpublished)* 

Follow-up year	relapse rate %	95% confidence interval
1 st	3.4	2.0 -5.8
$2^{nd}$	4.7	3.0-7.5
3 rd	5.1	3.2-8.1
4 th	4.7	2.9-7.8
5 th	2.1	0.9-4.6
$6^{\text{th}}$ to $8^{\text{th}}$	2.2	1.4-3.0

Based on EUROCARE data we estimate that the 5-year distant recurrences plus second ipsilateral or contralateral BC for patients recruited in the first few years after diagnosis will be about 20%. In the subgroup of patients selected on the basis of high insulin and/or testosterone levels (50% of cases with RR of the order of 3), we estimate that about 30% of patients will develop a recurrence or a second primary BC within 5-year follow-up: 360 cases out of 1200. Considering that the WINS randomized study obtained a 24% reduction of recurrence rate changing a single dietary factor (total fat) (39), and that observational studies suggested that a moderate physical activity may reduce recurrence rate by over 40% (28), we hypothesize that a comprehensive dietary intervention plus physical activity will reduce BC recurrence rate by 33% or more, but we consider also a more prudent estimate of 25% reduction.

The following table gives the number of patients (per arm) that we should recruit in order to have 90% or 80% power to detect a significant difference with  $\alpha < 0.05$ , two sided, or one sided ( $\alpha < 0.10$ ).

Power (1-β)	0.9	0.9	0.8	0.8
α	0.05	0.10	0.05	0.10
33% reduction	412	339	313	251
25% reduction	748	614	566	451

Our aim is to recruit 1,200 high risk patients in order to have 600 patients per arm, which shall guarantee 80% chance of getting a significant difference also with 25% reduction, and allowing for 90% compliance in the intervention group and 10% contamination of the control group.

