#### Insulin and related metabolic factors effect BC risk

Overweight and sedentary lifestyle are associated with insulin resistance. Women who gain weight in adulthood and overweight postmenopausal women have a greater risk for BC than lean women (11, 12). Postmenopausal women who engage in regular exercise (> 3 hours per week) have a reduced risk for BC compared with inactive women (13, 14). Several epidemiological studies found that high serum insulin and IGF-I levels are associated with increase BC risk (15-20), with, however, some inconsistencies as for the effect modification of age and menopausal status.

Insulin and testosterone effect prognosis in BC patients

In BC patients, high serum levels of insulin (21) and testosterone (22 and Micheli et al, submitted) are significantly associated with increased risk of recurrences; after adjustment for traditional prognostic factors (cancer stage at diagnosis, ER and PR) the RRs for BMI and for insulin in the upper quartile were about 2, while the RRs for testosterone in the upper tercile ranged from 2 to 7. We also found a borderline significant association of ER+ cancer with serum levels of estradiol, which, however, disappeared upon adjustment for testosterone levels (22). Testosterone levels are higher than estradiol levels, are easier to measure reproducibly and have lower intra- individual variability (23-25). For this reason, and because it proved to be predictive at any age, we chose testosterone as the main hormonal indicator of BC risk.

We also showed an high risk of recurrence in patients with metabolic syndrome, defined as the presence of three or more of the following factors: abdominal obesity (waist circumference >88 cm), hypertension (SBP>130 and /or DBP >85), hyperglycemia (>110mg/100ml), high triglycerides (>150 mg/100ml) or low HDL cholesterol (<50 mg/100ml) (26) (Table 1). Consistently, several observational studies suggested that sedentary habits (28) and overweight (27) are associated with increased BC incidence and BC recurrences.

Table 1. Hazard ratio of developing recurrences during 5.5-year follow-up of 110 BC patients according to the presence or absence of metabolic syndrome and serum testosterone levels above or under the median value (26).

Metabolic	Testosterone	Recurrence		Hazard	95% C.I
syndrome	>0.40 ng/ml	Yes	No	Ratio	
No	No	7	46	1	
Yes	No	1	3	2.2	0.2-19.4
No	Yes	17	24	3.8	1.5-9.5
Yes	Yes	7	5	6.7	2.3-19.8

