#### Study aims and design

We propose a randomized intervention trial of diet and physical activity to reduce BC relapse (local, distant), and second ipsilateral or contralateral BC, in BC patients at high risk of recurrence because of biochemical markers of increased risk, namely high serum testosterone and/or high fasting insulin and/or metabolic syndrome. Several other markers of increased recurrence risk are available, such as cancer stage at diagnosis, histological grade, hormonal receptors and other gene expression profile. All these will be registered, but we are specifically interested in markers of the host that can be modified through life-style.

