## Identification of eligible patients

Inclusion criteria:

1) Mastectomy or conservative surgery for invasive breast carcinoma, any type, in the last five years (we expect to recruit mostly patients at the time of diagnosis or at the end of the first follow-up year after surgery, i.e when chemotherapy has been concluded and hormonal therapy, if necessary, started)

2) Absence of signs or symptoms suggestive of recurrences Presence of one or more of the following endocrine/metabolic indicators:

- serum testosterone level ≥ 0.4 ng/ml (1 nmol/ml), corresponding to the median value in BC patients, or
- serum insulin ≥ 7 uU/ml ( 50 pmol/L), corresponding to the upper quartile of insulin distribution in BC patients, or
- metabolic syndrome, present in about 15% of BC patients

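### The 30% five-year risk is not derived for the three-marker group enrolled, and the 80% power for a 25% reduction holds after the stated non-compliance and contamination only if 25% is already an intention-to-treat effect

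*Combined protocol and SAP*

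**What the plan says.** In 'Statistical power' the plan starts from an overall five-year risk of about 20%. It moves to the subgroup "selected on the basis of high insulin and/or testosterone levels (50% of cases with RR of the order of 3") and arrives at about 30%, or 360 events in 1,200 patients. The sample-size table follows. The section concludes that 600 per arm guarantees 80% power even for a 25% reduction, and that this allows for 90% compliance in the intervention arm and 10% contamination in the control arm. The opening summary repeats the 30%, and gives power of 80% for a 25% reduction and 90% for a 33% reduction.

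The enrolled group is defined more widely. 'Identification of eligible patients' requires "Presence of one or more of the following endocrine/metabolic indicators": testosterone at a cut-off "corresponding to the median value in BC patients", insulin at a cut-off "corresponding to the upper quartile of insulin distribution in BC patients", or "metabolic syndrome, present in about 15% of BC patients". 'Study aims and design' gives the same rule: "high serum testosterone and/or high fasting insulin and/or metabolic syndrome". The summary applies the 30% to this three-marker group.

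**The concern.** There are two problems with the same power statement.

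First, a rule that admits patients on any marker cannot select fewer than its commonest marker does. Testosterone at or above the median already gives about 50%. A share of exactly 50% would require every high-insulin patient and every metabolic-syndrome patient also to have high testosterone. If the overall risk is fixed, a larger eligible share pulls that group's risk towards the overall average unless its relative risk rises. The 30% feeds the whole sample-size table and both statements of 80% power.

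Second, the plan says the 80% allows for imperfect compliance and contamination, but does not say whether 25% is the effect under full adherence or the effect expected by intention to treat. The table gives 566 per arm for this case and the plan takes 600, a margin of 6% (600/566 = 1.06). The size of that margin can be checked against the dilution it is meant to cover.

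**Working it through.** Power is shown as uncorrected/continuity-corrected, two-sided 0.05, 600 per arm.

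**1. The plan's own figures.** With overall risk 20%, share f and relative risk RR, the eligible group's risk is 0.20·RR / (1 + (RR − 1)·f). At f = 0.50 and RR = 3 this is 0.60/2 = 30%, as stated. The continuity-corrected two-proportion formula for 30% v 20% and 30% v 22.5% gives 412/339/313/251 and 748/614/566/451, which are all eight table entries. Power for 30% v 22.5% is 84/82%.

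**2. The share under the enrolment rule.** Table 1, in the section on insulin and prognosis ("Hazard ratio of developing recurrences during 5.5-year follow-up of 110 BC patients according to the presence or absence of metabolic syndrome" and testosterone), gives:
- Testosterone above 0.40 ng/ml: (17 + 24 + 7 + 5)/110 = 53/110 = 48.2%.
- Testosterone or metabolic syndrome: 53 + 4 = 57, and 57/110 = 51.8%, before insulin is counted.

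The documents do not give the overlap of insulin with the other two markers. Assumed values:
- 75% of high-insulin patients already qualify: 0.518 + 0.25 × 0.25 = 58%.
- Insulin independent of the other two: 0.518 + 0.25 × 53/110 = 64%.

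**3. The relative risk in the widened group.** Table 1's crude RR for testosterone or metabolic syndrome is (25/57)/(7/53) = 3.3. At a share of 51.8% the formula gives 30.2%, so adding metabolic syndrome alone does not take the risk below 30%.

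To add insulin, start from this group and add insulin-only patients, share g = f − 0.518, at RR 2 against those still ineligible. The same section of the plan reports an RR of about 2 for upper-quartile insulin. Set the mean risk of the 48.2% not yet eligible to 1. The remainder then has risk u = 0.482/((1 − f) + 2g), and the eligible group's mean is (0.518 × 3.32 + 2g·u)/f.

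| Share f | u | Eligible mean | RR (mean/u) | Risk | Power, 25% reduction |
|---|---|---|---|---|---|
| 58% | 0.886 | 3.16 | 3.6 | 28.7% | 82/80% |
| 64% | 0.798 | 2.99 | 3.7 | 27.2% | 79/77% |

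With RR simply held at 3, the risks would be 27.8% (80/78%) and 26.3% (77/75%). The risk at which power is exactly 80% is 27.7% uncorrected and 28.7% corrected.

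**4. The compliance and contamination allowance.** Let p be the undiluted control risk and r the full-adherence reduction. Control rate = 0.9p + 0.1p(1 − r); intervention rate = 0.9p(1 − r) + 0.1p. At the plan's own p = 0.30 and r = 0.25:
- Control: 0.27 + 0.0225 = 29.25%.
- Intervention: 0.2025 + 0.03 = 23.25%.
- Difference: 6.0 points instead of 7.5. Power is 66/63%, and 80% would need about 843/876 per arm.

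If 25% is already the intention-to-treat effect, the comparison stays 30% v 22.5% and power stays 84/82%.

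**5. The 33% hypothesis (taken as one third, as the plan's table does).** At 30%, power is 98/98% undiluted and 89/88% diluted. At a 64% share with RR 3 it is 96/95% undiluted.

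**The case against.** A reader might infer from the share alone that the trial is underpowered for a 25% reduction. The documents do not support that, for four reasons.

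- **Marker data.** The only joint marker data they contain return 30.2%. The 58% and 64% shares are assumptions. The plan's account of insulin stimulating androgen synthesis argues for overlap, which puts 64% towards the pessimistic end.
- **Relative risk.** The RR may be higher than 3. The plan reports that "the RRs for testosterone in the upper tercile ranged from 2 to 7". At a 58% share, RR 5 gives 30.1% and power of 84/83%; at 64%, RR 7 gives 28.9% and 82/80%. Holding RR at 3 as the group widens is not neutral either: moving raised-risk patients out of the comparison group lowers that group's risk, as the table above shows.
- **Base risk.** As worded, the 20% counts distant recurrence and second breast cancers, while 'Follow-up and outcome events' also counts local/regional recurrence. The wording is ambiguous, because Table 4 is headed local plus distant. With a base of 22% and RR 3, the risk is 30.6% at a 58% share and 28.9% at 64%, and power is at least 80% in both.
- **Existing check.** The milestones already compare observed with expected recurrences at month 24.

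All of this stands, and it limits the first problem to an untested planning input. A reader might also take it for a calculation error; it is not one, since the table is right for its inputs.

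Two things remain. The share used is still the lowest the rule allows, so a single 30% cannot carry a guarantee. And none of these points answers the dilution question, which arises at the plan's own 30%.

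**Conclusion.** The point holds in two parts, and is minor to moderate.

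**Risk.** The 30% was derived for a share of 50% and a description naming two markers, then applied to a three-marker group whose share exceeds 50%. A shortfall is possible but not shown. If the overall risk is 20% and insulin-only patients have RR about 2, undiluted power for a 25% reduction is about 82/80% at a 58% share and 79/77% at 64%. A higher RR, or a base risk that includes local recurrence, would restore 80%.

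**Allowance.** The 80% after 90% compliance and 10% contamination does not hold if 25% is the full-adherence effect: power is 66/63%. If 25% is the intention-to-treat effect, power is 84/82% and the allowance adds nothing. The plain sense of the sentence is the first, but the plan does not say, so it would go too far to call the 80% simply wrong.

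The 33% reduction, which is the main hypothesis, keeps high power undiluted and close to 90% when diluted at the plan's own 30%.

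**What to change.** 1. State whether 25% and 33% are full-adherence or intention-to-treat effects. Restate the power in the summary and in 'Statistical power' accordingly, and drop the guarantee.
2. Re-derive the eligible share, RR and control risk for patients meeting any of the three markers, with the base risk on the same event definition as the main outcome. Show power over a range of control risks, for example 26% to 32%. By the formula above, undiluted power for a 25% reduction is 77/75% at 26%, 81/79% at 28%, 84/82% at 30% and 87/86% at 32%. The markers measured at recruitment and the followed-up low-risk group allow the share and RR to be checked as the trial proceeds.
3. Base the expected number in the month-24 comparison on the re-derived risk, so that observed events are judged against the group actually enrolled.

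The cost is a recalculation, a short table and a few sentences. Enrolment, eligibility and follow-up do not change. The downside is a less favourable stated power for the 25% case.

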We now propose a randomized dietary and physical activity intervention trial to reduce BC recurrences (local, distant, or second BC) in BC patients at high risk because of high serum testosterone (>0.4 ng/ml), or insulin (>50 pmol/L), or the presence of metabolic syndrome. In these patients the estimated 5-year cumulative recurrence rate is 30%. Participants will be recruited through hospitals, patients' associations, and the media. We plan to recruit 1,200 patients and to randomize them in two groups: 600 shall receive standard recommendation for healthy lifestyle without, however, any active support; 600 shall receive a combination of individual and group contacts over the course of one year, including kitchen courses, gym and dance classes, common meals and reinforcing meetings, with emphasis on a comprehensive dietary change including low saturated fat and low refined carbohydrates, and high whole grain cereals and pulses consumption. Compliance will be monitored through weight change and plasma glucose, triglycerides, cholesterol and testosterone.

The main analysis will be by intention to treat. Under the hypothesis of reducing recurrence rate by 25% or 33% the statistical power of the study is 80% or, respectively, 90%, (P<0.05, 5-year follow-up).

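### With the plan's own 90% compliance and 10% contamination, 600 per arm gives about 63–66% power for a 25% reduction, not 80%

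*Combined protocol and SAP*

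**What the plan says.** The Statistical power section sets the event rate ("we estimate that about 30% of patients will develop a recurrence or a second primary BC within 5-year follow-up: 360 cases out of 1200"), hypothesises that the intervention "will reduce BC recurrence rate by 33% or more", and adds a cautious alternative ("but we consider also a more prudent estimate of 25% reduction"). A table then gives patients per arm for 90% and 80% power at α 0.05 and 0.10: 412, 313 (α 0.05) and 339, 251 (α 0.10) for the 33% reduction; 748, 566 and 614, 451 for the 25% reduction.

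The section closes by choosing 600 per arm and gives this reason: "which shall guarantee 80% chance of getting a significant difference also with 25% reduction, and allowing for 90% compliance in the intervention group". It names a second allowance, "10% contamination of the control group".

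The opening summary, at the end of the first Background section, says that under the hypothesis of "reducing recurrence rate by 25% or 33% the statistical power of the study is 80% or, respectively, 90" per cent ("P<0.05, 5-year follow-up"). It does not mention compliance or contamination.

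The Statistical analysis section makes intention to treat the main analysis. The section on control of potential biases expects compliance above 90% and some change of habits among controls.

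**The concern.** The last sentence of the power section claims that 600 per arm absorbs two sources of dilution and still leaves 80% power for a 25% reduction. Yet 600 is only 34 more than the table's 566, and no diluted risk, diluted effect or inflated sample size appears anywhere. Non-compliance and contamination shrink the difference between the arms, and the required sample size grows with the inverse square of that difference. A 6% margin is therefore unlikely to cover both.

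This matters because intention to treat tests the diluted contrast. If the power is overstated, the chance of missing a real 25% effect is understated. A reader of a null result would also take from the plan that such an effect had been tested with 80% power under realistic adherence.

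**Working it through.** **Inputs** (Statistical power section unless noted): control 5-year risk 0.30; reduction 25% (0.225) or one third (0.20); α 0.05 two-sided; n = 600 per arm; compliance 90%; contamination 10%; analysis by assigned arm (Statistical analysis section).

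**Step 1: reproduce the table.** For risks p₁ and p₂, difference d and mean risk p̄:

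n = [z_α √(2p̄(1−p̄)) + z_β √(p₁(1−p₁)+p₂(1−p₂))]² / d²

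Continuity-corrected: n_c = (n/4)·[1 + √(1 + 4/(n·d))]²

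For 0.30 vs 0.225, with p̄ = 0.2625, α 0.05 and 80% power:
- n = (1.960×0.6222 + 0.842×0.6200)² / 0.075² = 539.1
- n_c = 565.4, rounded up to **566**, as stated.

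The same formula gives all eight entries exactly: 412, 339, 313, 251 and 748, 614, 566, 451. The α 0.10 columns match two-sided 0.10, that is one-sided 0.05. Every match uses full compliance and no contamination, so the table has no allowance in it.

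**Step 2: apply the plan's two figures.** Assume that non-compliers get no effect and contaminated controls get the full effect.
- Intervention: 0.9×0.225 + 0.1×0.30 = 0.2325
- Control: 0.9×0.30 + 0.1×0.225 = 0.2925
- Difference: 0.060 instead of 0.075; relative reduction 20.5% instead of 25%

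**Step 3: power at 600 per arm.**

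Power = Φ{[d − z_α √(2p̄(1−p̄)/n)] / √[(p₁(1−p₁)+p₂(1−p₂))/n]}

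- = Φ{[0.060 − 1.960×0.02540] / 0.02534} = Φ(0.403) = **65.6%**
- With continuity correction, d is reduced by 1/600: Φ(0.337) = **63.2%**

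| 25% reduction, n = 600, two-sided 0.05 | Risks | Power | Continuity-corrected |
|---|---|---|---|
| No dilution | 30.00% vs 22.50% | 84.0% | 82.4% |
| Non-compliance only | 30.00% vs 23.25% | 75.4% | 73.3% |
| Contamination only | 29.25% vs 22.50% | 76.2% | 74.1% |
| Both, as the plan states | 29.25% vs 23.25% | 65.6% | 63.2% |

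A log-rank check (Schoenfeld) with both allowances uses HR = ln(1−0.2325)/ln(1−0.2925) = 0.765 and 600×(0.2925+0.2325) = 315 events. It gives 66.3%.

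**Step 4: sample size for 80% power with both allowances.** The formula of Step 1 at 0.2925 vs 0.2325 gives 843 per arm, or 876 corrected. The corrected figure is 876/566 = 1.55 times the table entry. The plan uses 600/566 = 1.06 times.

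**Step 5: the one-third reduction.** Diluted risks are 0.29 and 0.21. Power at 600 per arm is 89.4% (88.1% corrected), against 98.0% (97.7%) undiluted. Taking the reduction as exactly 33% gives 88.7% (87.4%) diluted.

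**Step 6: smallest effect with 80% power.** A full-compliance reduction of 30% gives diluted risks of 29.1% and 21.9% and power of 81.7% (79.9%). The threshold is therefore about 30%.

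**The case against.** **The 25% may already be a net effect.** If it is the reduction expected by intention to treat, 600 per arm gives 82–84%. The main 33% hypothesis, diluted, is a net reduction of 27.6% and keeps 88–89%. The plan also sets its effect sizes beside a 24% reduction from a randomised diet trial, which may itself be an as-randomised figure. However, the section presents 25% as a more cautious estimate of the intervention's effect and then states the allowances in addition to it. If 25% is net, the sentence allows for nothing further and is still wrong as written.

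**The dilution model is not in the documents.** This stands, so the exact figure depends on an assumption. Variants for a 25% reduction at 600 per arm (two-sided 0.05 unless noted):
- 95% compliance with 10% contamination: 69–71%
- non-compliers and contaminated controls each getting half the effect: 74–76%
- 30% read as the pooled rate (360 of 1,200, so control 34.3%): 72–74%
- 30% read as the already contaminated control rate: 65–67%
- 25% read as a hazard ratio of 0.75, diluted to (0.9×0.75+0.1)/(0.9+0.1×0.75) = 0.795, with 315–360 events: 53–59%
- α 0.10 ("two sided, or one sided" leaves sidedness open): 74–76%

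None reaches 80%. Treating non-compliers as lost patients (540 per arm) gives 78–80%, but this omits contamination and conflicts with intention to treat.

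**The opening summary claims no allowance.** Undiluted, its 80% is a fair lower bound. But its pair of figures fits no single basis: the design gives 82–84% and about 98% undiluted, or 63–66% and 87–89% diluted. It should be restated on the same footing as the power section.

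**The planned analysis is a covariate-adjusted Cox model.** True, but the unadjusted log-rank check agrees with the two-proportion result.

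**Conclusion.** The concern holds. The stated 80% for a 25% reduction is the undiluted figure, presented as though it included both allowances. Under the plan's own compliance and contamination figures, power is about 63–66%, so the chance of missing a true 25% effect is 34–37% rather than 20%. Either allowance alone already takes power below 80%.

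The figure rests on linear, all-or-nothing dilution and on 30% as the uncontaminated control risk, which is how the table itself uses it. Other readings that apply both allowances move it within roughly 53–76%, and none rescues the claim. The shortfall is specific to the 25% case, which is the case used to justify 600 per arm. For the 33% hypothesis, the 90% in the opening summary roughly stands after dilution.

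**What to change.** Restate the power in the final sentence of the Statistical power section and in the opening summary, on one declared basis:
- With 600 per arm, two-sided α 0.05, 90% compliance and 10% contamination, power is about 65% for a 25% reduction and 87–89% for 33%.
- The smallest full-compliance reduction detectable with 80% power is about 30%.
- Show the diluted risks (29.25% vs 23.25%) next to the table, label the table entries as undiluted, and state the dilution model as an assumption.
- If 25% was meant as a net intention-to-treat effect, say so and remove the claim of further allowances.

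This is a wording change. It makes the stated power less favourable and needs no extra patients. Keeping the 80% claim as written would instead need 843–876 per arm, that is 1,686–1,752 in total against the planned 1,200.

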#### Previous randomized dietary intervention trials to decrease BC recurrences

Two randomized trials carried out in the eighties on a small number of BC cases (about 100 each) suggested that calorie restriction may reduce BC recurrences (41) and total mortality (42). The Women's Intervention Nutrition Study (WINS), a large randomized controlled trial investigating the role of dietary fat reduction on relapse-free survival in postmenopausal women with early-stage resect able BC (n = 2,700), found that patients on the reduced-fat diet had a lower risk of recurrence (hazard ratio = 0.76, 95% CI = 0.60-0.98) than women on the standard diet (39). A further large-scale trial aimed at reducing fat and increasing fruit and vegetable intake in women diagnosed with BC is currently ongoing (43).

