### Statistical analysis

We shall first assess the baseline association between androgens, insulin, and several measures of adiposity including body mass index, waist circumference and (in a sample of cases) percentage body fat, with Spearman correlation coefficients. We shall then compare the change in food consumption, body weight, and geometric means of hormone end points from baseline to 12 months in the intervention and control group.

The main analysis of the intervention effect on the incidence of recurrences will be by intention to treat, i.e. based on assigned treatment at the time of randomization, regardless of adherence. As a secondary analysis we shall assess the effect by change in body weight and biomarkers. We shall compute total survival, disease free survival and relapse free survival.

Hazard ratios and confidence intervals will be computed by the Cox proportional hazard model, with standard clinical-pathological prognostic covariates as potential confounders. Separate analyses will be carried out by ER, PR and erbB2 status. Interim analyses will be carried out as soon as the total follow-up person-years reach 2,500 (corresponding to  $\alpha$  =0.10 and  $\beta$ = 0.20 for a 33% reduction of recurrence rate).

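### With the compliance and contamination the plan itself allows for, 600 per arm does not give 80% power for a 25% reduction on either the risk or the hazard scale

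*Combined protocol and SAP*

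**What the plan says.** The opening summary (first Background heading) gives a 5-year cumulative recurrence rate of 30% in the high-risk group. It then states: "Under the hypothesis of reducing recurrence rate by 25% or 33% the statistical power of the study is 80% or, respectively, 90" per cent ("P<0.05, 5-year follow-up").

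The Statistical power section supports a reduction of a third or more with two sources. One is the low-fat diet trial ("Considering that the WINS randomized study obtained a 24% reduction of recurrence rate"); the other is observational work on physical activity suggesting a reduction of over 40%. It then adds the second scenario: "but we consider also a more prudent estimate of 25% reduction". Its table gives 566 per arm for a 25% reduction at 80% power and α = 0.05, and the α labels are introduced as "two sided, or one sided". The section ends with 600 per arm, "which shall guarantee 80% chance of getting a significant difference also with 25% reduction", with 90% compliance in the intervention group and 10% contamination among controls allowed for.

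The section on previous dietary trials reports the low-fat trial's result as "hazard ratio = 0.76, 95% CI = 0.60-0.98". For the main comparison, the Statistical analysis section says: "Hazard ratios and confidence intervals will be computed by the Cox proportional hazard model", by intention to treat.

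**The concern.** Two things have to be settled before the 80% can be relied on.

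The first is the allowance. The sentence promises 80% with imperfect compliance and contamination already covered. Yet 600 exceeds the tabulated 566 by only 6% (600/566 = 1.06). If 10% of each arm in effect behaves like the other arm, the risk difference shrinks to 0.9 - 0.1 = 0.8 of its full size. The required sample then grows by roughly 1/0.8² = 1.56.

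The second is the scale. A 25% reduction in 5-year risk and a 25% reduction in hazard are different effects when control risk is 30%, and the plan does not say which it means.

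At stake is how a non-significant result would be read. A reader who trusts the 80% would put the chance of missing a true 25% reduction at 20%. The design's actual chance of missing it is larger.

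**Working it through.** **Inputs.** Control 5-year risk 30% (summary; Statistical power). 600 per arm, 1:1. Two-sided α = 0.05. Reductions of 25% and 33%. 90% compliance and 10% contamination. Low-fat trial hazard ratio (HR) 0.76. The plan gives no dropout or competing-risk rate, and none is assumed.

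**1. Reproducing the table.** Two-proportion formula with continuity correction, p₁ = 0.30, p₂ = 0.225, d = 0.075, p̄ = 0.2625:
- n′ = [1.96√(2 × 0.2625 × 0.7375) + 0.8416√(0.30 × 0.70 + 0.225 × 0.775)]² / 0.075² = 539.1
- n = (n′/4)[1 + √(1 + 4/(n′d))]² = 565.4, rounded up to **566**, as tabulated.

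With p₂ = 0.20 for the 33% row, all eight cells match (412, 339, 313, 251; 748, 614, 566, 451). So the table applies the reduction to cumulative risk. Under proportional hazards the equivalents are:
- 25%: HR = ln 0.775 / ln 0.70 = 0.715
- 33%: HR = ln 0.80 / ln 0.70 = 0.626

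**2. Risk scale, 600 per arm, no dilution (30% v 22.5%).**
- Two proportions: Φ[(0.075√600 - 1.96 × 0.6222)/0.6200] = 84.0%; with continuity correction 82.4%.
- Log-rank/Cox: events = 600 × (0.30 + 0.225) = 315; Φ[√(315/4) × |ln 0.715| - 1.96] = 84.7%.

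**3. Risk scale with the stated allowance.** Assumption: non-compliers carry the control risk, contaminated controls the intervention risk.
- Intervention: 0.9 × 0.225 + 0.1 × 0.30 = 0.2325
- Control: 0.9 × 0.30 + 0.1 × 0.225 = 0.2925
- Two proportions: Φ[(0.06√600 - 1.96 × 0.6222)/0.6208] = 65.6%; with continuity correction 63.2%.
- Log-rank: HR = ln 0.7675 / ln 0.7075 = 0.765; 315 events; power 66.3%.

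**4. Hazard scale, HR 0.75.**
- Intervention risk = 1 - 0.70^0.75 = 0.2347, a relative risk reduction of 21.8%.
- Expected events = 600 × (0.30 + 0.2347) = 321. Needed for 80%: 4(1.96 + 0.8416)²/(ln 0.75)² = 379.
- Log-rank power: Φ[√(321/4) × 0.2877 - 1.96] = 73.1%. Two proportions 72.5%; with continuity correction 70.2%. A log-rank simulation of 8,000 runs gave 73.3%.
- At the low-fat trial's own HR of 0.76: 69%.
- With the allowance, risks are 0.9 × 0.2347 + 0.1 × 0.30 = 0.2412 and 0.9 × 0.30 + 0.1 × 0.2347 = 0.2935. HR = ln 0.7588 / ln 0.7065 = 0.795. Power is 53.9% (log-rank), 53.4% (two proportions) and 50.8% (continuity-corrected).

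**5. The 33% scenario.**
- Risk scale (30% v 20%): about 98% undiluted. Diluted risks are 21% v 29%, with power 88-90%.
- HR 0.67, log-rank: about 94% undiluted and 80% diluted.

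| Scenario | Undiluted | With allowance |
|---|---|---|
| 30% to 22.5% (HR 0.715) | 82-85% | 63-66% |
| HR 0.75 | 70-73% | 51-54% |
| 30% to 20% (HR 0.626) | 98% | 88-90% |
| HR 0.67 | 94% | 80% |

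**The case against.** The strongest defence is that the table contains no mistake, and that stands. Every cell reproduces, and sizing on proportions while analysing by Cox costs no power here (82-84% against 85%).

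A reader might infer that the authors meant HR 0.75, took it from the low-fat trial, and then sized the trial on an easier scale. The documents do not support that:
- The summary calls the 30% a cumulative rate and speaks of reducing the recurrence rate directly afterwards. The first Background section describes the low-fat result as fewer recurrences over 5 years.
- The interim trigger of 2,500 person-years for a 33% reduction matches the table's 251-per-arm cell (2 × 251 × 5 = 2,510), which is a cumulative-risk calculation.
- The 24% is offered in support of a reduction of a third or more. The 25% is added as a cautious alternative with no derivation.

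The cumulative reading is therefore the better supported one. What remains is that the scale is unstated, while the cited result and the planned analysis are both on the hazard scale.

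Nor are the 360 cases an error in the sizing. That figure is 30% of 1,200 before any effect is introduced, and the table does not use it.

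One could also suppose that 25% is already net of dilution, since a 33% cut diluted as above leaves (0.29 - 0.21)/0.29 = 27.6%. The text does not say so. It presents 25% as a cautious estimate of the intervention's effect and adds the allowance to it.

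Finally, the commitment to confidence intervals reduces the risk of over-reading a null result. It does not make the stated power correct.

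**Conclusion.** The claim of 80% power for a 25% reduction, with 90% compliance and 10% contamination allowed for, is not met. On the scale the table uses, the figure is about 63-66%. Read as HR 0.75, it is about 51-54%. Without the allowance, the claim holds on the risk scale (82-85%) but not on the hazard scale (70-73%). The summary's 90% for a 33% reduction is close to right on the risk scale with dilution (88-90%).

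These figures assume 30% control risk at 5 years, two-sided α = 0.05, proportional hazards and no dropout. The diluted figures also assume a full exchange of risk for non-compliers and contaminated controls. The plan does not define either term; if the exchange is only partial, power lies between the two columns of the table. Longer follow-up would add events.

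**What to change.** In the opening summary and the Statistical power section:

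- State that 25% and 33% mean 5-year risks of 30% to 22.5% and 30% to 20% (HR 0.715 and 0.626).
- Replace the 80% claim with power at 600 per arm under the stated compliance and contamination: about 63-66% and 88-90%. State the dilution assumption behind these figures.
- Give the hazard-scale figures alongside: HR 0.75, about 73% undiluted and 54% diluted; HR 0.67, about 94% and 80%.

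Naming the scale without changing the 80% is not enough, because the sentence would still claim an allowance that 600 per arm does not carry. The change is one of wording. It makes the stated power less favourable and needs no extra patients.
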